[figure not shown]

SYNOPSIS (English)	
Title	Pain monitoring after breast biopsy: benefit of e-health
Acronym	BIO-PSY
Pathology	Breast cancer
Protocol codes	Sponsor Code : PRO ICM 2020-06 BIO ID-RCB: 2020-A00836-33 N° NCT : NCT04456920
Study Sponsor	Institut régional du Cancer de Montpellier - ICM Clinical Research and Innovation Department (DRCI) [name] – France Contact Name : Mme [name] Mail : [contact] [contact] [contact]
Clinical trial coordinators	[name] [name] ICM Department of Radiology [contact] E-mail : [contact] Clinical trial co-coordinator : [name] [name], Ph.D ICM Department of Supportive Care [contact] E-mail : [contact]
Methodology and data management Center	Institut régional du Cancer de Montpellier - ICM Biometrics Unit Contact : Mme [name] [contact] E-mail : [contact]
Project manager	Institut régional du Cancer de Montpellier - ICM DRCI - Promotion Unit Contacts : [name] [name] [contact] E-mail : [contact]
Study design	Monocentric, prospective, open-labeled, randomized controlled trial
Trial sites	1 participating center
Number of planned patients	Expected number of patients : 192

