Background and Rationale	
Each year, approximately 1500 breast biopsies (1000 microbiopsies and 500 macrobiopsies) are performed in the radiologic department of the Montpellier Cancer Institute (ICM). This exam, which is relatively easy for the radiologist, can however lead to major anxiety for patients. Indeed, previous studies show that about 50% of women undergoing a breast biopsy have significant anxiety affects. Anxiety associated with the risks of biopsy, potential breast cancer diagnosis and/or lack of routine sedation procedures increase patient concerns. Distress prior to biopsy is associated with greater pain and discomfort during the procedure. The psychological distress that persists after the biopsy is related to a worse psychological management of side effects of the biopsy breast (e.g., sensitivity, skin irritation).
 
Limiting apprehension, worry and anxiety induced by the uncertainty linked to the biopsy results and the biopsy-related pain should be an integral part of the medical care through the patient follow-up during, after and until the diagnosis is announced. In light of these challenges, new alternative methods are emerging to enhance patient knowledge, develop procedural skills, improve confidence and mitigate procedural anxiety. However, to our knowledge, few methods have been developed during this period of 'waiting-time'. Currently, only care instructions and a consultation to announce the results (about 10 days after the procedure) are proposed to patients at the end of biopsy. Patients are also encouraged to call if they suspect complications such as infection or bleeding.
 
In this context, we propose to integrate a pain management after biopsy via e-health system through the patient's medical care. Radiologist/patient communication could have an impact on patients' anxiety and health-related issues, given the challenging nature of discussions around need for breast biopsy and potential implications of the results. Indeed, paying attention and focusing on symptoms as patients experience them improves their empowerment and their adjustment to the disease.
 
Web-based systems that can provide electronic-Patient reported Outcomes (e-PRO) have been shown to prompt clinicians to intensify symptom management, to improve symptom control and to enhance patient-clinician communication patient satisfaction, as well as well-being. In addition, it is known that improved communication between patients and medical staff to less anxiety after a biopsy and that anxiety is related to pain.
 
Taken as a whole, these elements encourage the integration of e-health and e-PRO for the management of pain and anxiety in patients undergoing a biopsy. The benefits of e-PRO are still being discussed in terms of quality of life (Qol) and psychological distress. We thus propose to integrate two types of e-health intervention: 1/e-PRO collected by connected objects (smartphone or tablet) as they were used in previous studies, and 2/ e-PRO collected by a phone consultation, which values human communication between the medical staff and the patient.
 
In case of significant pain, the collection of e-PRO by any of these e-health interventions will generate an alert and a reactive and responsive care.
 
In fine, the purpose of this research is to improve the medical organization and care of post-biopsy patients by proposing an innovative connected patient technology, regardless of their remoteness from the hospital.
 
Social inequalities will be reduced by lending a tablet to patients who do not have such a device with a 4G key.

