Statistical considerations	
Sample size.
 
A pilot study has been performed in the radiology department including 25 patients in order to determine the pain level on average: mean = 5 and standard deviation = 3.
 
Assuming a mean pain score on day 4 equals to 5 points with a standard deviation equals to 3 in the control group, with α (two-sided) = 2.5%, power= 90%, it is necessary to include 58 patients per group (174 patients in total), to detect a difference of 2 points (according algology criteria and good practice recommendations) between control arm and each experimental arm. Finally, 192 patients will be included considering 10% non-evaluable patients.
 
Statistical analyses.
 
A statistical analysis plan (SAP) will be written before the closed database. All statistical analyses will be performed on ITT population and on PP (per-protocole) population for primary endpoint. All collected data will be described.
 
Descriptive analyses will be performed using frequency (N) and percentage (%) for categorical variables, mean / standard deviation or median / range for continuous parameters.

	
The Pearson's chi-square or the Fisher's exact test will be performed for categorical variables and the Student test or Wilcoxon / Kruskal-Wallis test for continuous parameters.
 
The primary endpoint, pain score assessed by phone 4 days after biopsy, will be compared between control and experimental arms (telemedicine vs control and smartphone vs control).
 
The secondary endpoints will be compared between control and experimental arms (telemedicine vs control and smartphone vs control) and between the two e-PRO interventions (telemedicine vs smartphone).
 
All statistical analyses will be performed with the Stata software v16.0 and a statistical report will be provided according to the current model.

Study period	
Starting date of inclusion: February 2021 Duration of inclusion: 34 months Duration of participation: 10 days (+/- 2 days) Date of end of patient follow-up: December 2023

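### Holm's procedure instead of a fixed 2.5% for each primary comparison would raise the chance of showing both e-health formats effective from 84% to 90%, with no extra patients, if both truly lower pain by 2 points

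*Combined protocol and SAP*

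**What the plan says.** The Background section explains why there are two experimental arms: "We thus propose to integrate two types of e-health intervention", one by phone consultation and one by connected object. The Sample size paragraph under Statistical considerations takes a control mean of 5 and SD of 3 and states "with α (two-sided) = 2.5%, power= 90%, it is necessary to include 58 patients per group (174 patients in total". The stated aim is "to detect a difference of 2 points (according algology criteria and good practice recommendations) between control arm and each experimental arm". Allowing for 10% non-evaluable patients, 192 are to be randomised 1:1:1, which is 64 per arm.

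Under Statistical analyses, "The primary endpoint, pain score assessed by phone 4 days after biopsy, will be compared between control and experimental arms", and the text in brackets names two comparisons, each format against control. For continuous outcomes it offers "the Student test or Wilcoxon / Kruskal-Wallis test for continuous parameters". It gives no significance level for the primary tests, no family-wise level and no multiplicity procedure. It does not say whether success means one positive comparison or two. On timing: "A statistical analysis plan (SAP) will be written before the closed database".

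**The concern.** The only significance level in the document is the 2.5% used for sizing. If the analysis simply carries it over, each comparison is judged at 2.5% regardless of the other. Suppose one format clearly succeeds and the other gives a p-value between 0.025 and 0.05. The fixed split then calls the second format negative, although a rule with the same 5% family-wise guarantee would call it positive.

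This matters because the trial was built to evaluate two formats. The planned 90% power applies to each comparison separately, and the chance of showing both is lower. The SAP has to state a decision rule in any case, so choosing the better one costs almost nothing.

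**Working it through.** **Inputs.** From Sample size: difference 2, SD 3, two-sided 2.5%, power 90%, 58 evaluable per group. From Treatment modalities: 1:1:1 allocation, so the two tests share a control arm and have correlation 0.5. Assumption: SD 3 in the experimental arms too, since the document gives it for control only.

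**Step 1. The plan's own figure.** The normal formula n = 2(z₀.₉₈₇₅ + z₀.₉₀)²·SD²/δ² gives 2 × (2.241 + 1.282)² × 9/4 ≈ 55.9, so 56. The exact noncentral t calculation gives power 89.9% at 57 and 90.5% at 58. The planned 58 is reproduced. At two-sided 5% the normal formula gives 48, so 58 does rest on 2.5%.

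**Step 2. Error control of the fixed split.** The bound is 0.025 + 0.025 = 0.05. With a shared control and no true effect, the actual family error is about 4.7%. This is valid.

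**Step 3. Error control under Holm.** If neither format works, a false positive requires the smaller p-value to be below 0.025. That is the same event as under the fixed split, so the error is again about 4.7%. If exactly one format works, a false positive requires the p-value of the ineffective format to be below 0.05, which has probability at most 5%. The procedure uses only p-values, so it serves the Student and the Wilcoxon test alike.

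**Step 4. Power.** Simulation of 4 million trials per scenario, 58 per arm, normal data, pooled t tests on 114 degrees of freedom:

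| True effects (points) | Quantity | Fixed 2.5% | Holm |
|---|---|---|---|
| 2 and 2 | both shown | 83.9% | 90.0% |
| 2 and 2 | each arm | 90.4% | 93.5% |
| 2 and 2 | at least one | 97.0% | 97.0% |
| 2 and 1.5 | both shown | 63.5% | 73.6% |
| 1.5 and 1.5 | both shown | 51.2% | 62.3% |
| 2 and 0 | effective arm | 90.5% | 90.6% |
| 2 and 0 | ineffective arm (false positive) | 2.5% | 4.5% |
| 0 and 0 | any rejection | 4.7% | 4.7% |

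Cross-check for effects 2 and 2, using P(both) = 2 × P(each) − P(at least one): 2 × 0.904 − 0.970 = 0.838 for the fixed split and 2 × 0.935 − 0.970 = 0.900 for Holm. A separate simulation with 400,000 trials gave 84.1% and 90.2%.

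**Step 5. Equivalent sample size.** With effects 2 and 2, the fixed split shows both in 89.5% of trials at 66 per arm and 90.1% at 67. Matching Holm would take 3 × 67 = 201 evaluable patients instead of 174, that is, 27 more.

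**Step 6. Sensitivity to SD.** With 2-point effects and an SD of 2.5 in the experimental arms, both are shown in 91.0% (fixed) versus 94.8% (Holm). With an SD of 3.5 the figures are 74.8% versus 83.2%.

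**Step 7. What the added rejections look like.** With SD 3 the standard error is 3 × √(2/58) = 0.557. Significance needs an observed difference of 1.265 points at p = 0.025 and 1.104 at p = 0.05. Holm therefore adds results of roughly that size. With effects 2 and 2 they occur in 90.0% − 83.9% = 6.1% of trials. Their median estimate is 1.21 points, 95% lie between 1.04 and 1.39, and the largest was 1.64. For example, an observed 1.18 points has p = 0.036 and a 97.5% interval of 1.18 ± 1.265, or −0.09 to 2.45.

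**The case against.** The strongest reply is that nothing is broken. The fixed split is valid, the sample size holds, and sizing at 2.5% is compatible with using Holm at analysis. The document never says that the analysis will use a fixed split, so the 84% starting point is inferred; if the SAP already uses Holm, there is no gain. This stands as a caveat. It is also a reason to write the rule down, since none is stated.

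Second, the plan sets power per comparison and does not define success as showing both formats. On the plan's own metric the gain is about 3 percentage points (90.5% to 93.5%), and the chance of at least one success is unchanged. That is correct, and both metrics should be reported.

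Third, if all 64 randomised per arm prove evaluable, the fixed split already shows both in about 88.3% of trials and Holm in 93.1%. The gain is smaller but remains.

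Fourth, the added positives are modest. In the simulation with effects 2 and 2, none reached the 2-point target, and their 97.5% intervals include zero. This is a real cost and must be disclosed with the result.

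Finally, it may be too late. The design is "Monocentric, prospective, open-labeled, randomized controlled trial", and the Study period entry gives "Date of end of patient follow-up: December 2023". Writing the SAP before database closure does not show that nobody has looked at outcomes by arm. The recommendation is therefore conditional on that point.

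**Conclusion.** The point holds as an inexpensive improvement; the plan is not in error. Within the same 5% family-wise bound and at the same sample size, Holm adds about 6 percentage points to the chance of showing both formats when each truly lowers pain by 2 points. It adds about 10 to 11 points when one or both effects are 1.5. It adds essentially nothing when only one format works, and the ineffective format then carries a higher but still controlled false-positive risk.

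The figures assume t tests, 58 evaluable per arm and SD 3 in all arms unless varied above, and that the 2.5% was meant as an equal split of 5%.

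**What to change.** Before any outcome is examined by arm, add a paragraph to the SAP along these lines:

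> The two primary comparisons (phone versus control, connected objects versus control) are tested by Holm's procedure at a family-wise two-sided level of 5%. The smaller p-value is tested at 2.5%; if it is significant, the other is tested at 5%. The Holm decision governs. The 97.5% confidence intervals are descriptive and may include zero for the second rejected comparison.

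Date the paragraph and record that no outcome by arm had been seen. Report the estimated difference beside each verdict, because a comparison that passes only at the second step will usually show an effect well below 2 points. Keep 58 evaluable per arm and the 2.5% sizing basis.

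If outcomes have already been examined by arm, or the sponsor prefers intervals that always agree with the tests, state the fixed 2.5% split explicitly and keep it.

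The cost is one paragraph and no patients. The price in inference is the rise from 2.5% to about 4.5% in the false-positive rate of an ineffective format beside an effective one. In addition, the interval includes zero for the rejections that Holm adds: about 6% of trials with effects 2 and 2, 2% with 2 and 0, 10% with 2 and 1.5, and 11% with 1.5 and 1.5.

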	
At D1, D2 and D3, patients in the experimental group 1 will receive a call from a neuro-psychologist during which pain, anxiety and esthetical biopsy impact will be assessed using numeric or visual analog scales during a semi-direct interview. During this call, any adverse events related to the breast biopsy will also be noted, as well as the amount, nature and dose of analgesics, anxiolytics, anti-depressants, anti-inflammatory and hypnotics taken linked to the biopsy. If detected, pain or significative distress would be specifically managed.
 
Patients in the experimental group 2 will be asked by SMS or notification to connect to the application in order to complete online the numeric and visual analog scales of pain, anxiety and esthetical impact. Any adverse events related to the breast biopsy will also be noted online, as well as the amount, nature and dose of analgesics, anxiolytics, anti-depressants, anti-inflammatory and hypnotics taken for the biopsy. If detected, pain or significative distress would be specifically managed.
 
At D4 post biopsy, all patients (of the 3 groups) will receive a phone call from a neuro-psychologist to assess pain, anxiety and esthetical impact, using numeric scales, and to collect adverse events. If detected, pain or significative distress would be specifically managed.
 
And at D10 (+/- 3 days), all patients will have the consultation of biopsy results announcement. This visit will be held either on-site or by videoconference. At the beginning of this consultation, pain, anxiety and esthetical impact will be assessed using numeric scales. The adverse events related to the breast biopsy will be collected as well as the amount, nature and dose of analgesics, anxiolytics, anti-depressants, anti-inflammatory and hypnotics taken for the biopsy and its findings. Insomnia will be evaluated by the Insomnia Severity Index. If detected, pain or significative distress would be managed as usually in the center. If the consultation is to be done by telephone, it is essential that this data collection be done before the results are announced.

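### The primary ITT comparison is complete-case by default: no rule covers a missing D4 pain score, and the named tests cannot use the D0 and D10 pain scores scheduled in every arm

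*Combined protocol and SAP*

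**What the plan says.** All of this is in the synopsis.

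- **Analysis sets** (Statistical considerations, Statistical analyses): "All statistical analyses will be performed on ITT population and on PP (per-protocole) population for primary endpoint". Neither set is defined.
- **Tests** (same place): "the Student test or Wilcoxon / Kruskal-Wallis test for continuous parameters". No imputation, repeated-measures model, baseline adjustment or missing-data sensitivity analysis is named.
- **Sample size** (Statistical considerations, Sample size): "it is necessary to include 58 patients per group (174 patients in total"), and then "Finally, 192 patients will be included considering 10% non-evaluable patients". The term non-evaluable is not defined.
- **Primary measurement** (Treatment modalities): "At D4 post biopsy, all patients (of the 3 groups) will receive a phone call from a neuro-psychologist". No call window or call-back rule is given.
- **Other pain scores** (Treatment modalities): all three groups are also scored at D0 and at the start of the results consultation, at about D10. Only the two experimental groups are scored at D1 to D3.
- **SAP** (Statistical considerations): it is still to be written, before the database is closed.

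**The concern.** A two-sample or rank test on D4 pain cannot use a patient who has no D4 value. With no other rule, the analysis labelled ITT contains only the patients reached at D4.

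The design gives a reason why the patients reached may differ by arm. By D4, Group 1 has been due three calls from a neuro-psychologist and Group 2 has been prompted to use an application, while controls have had no scheduled contact since D0. If answering the D4 call is related to pain, and differently so in each arm, both primary comparisons are biased despite randomisation. Adding patients does not cure that. A patient who misses the D4 call may well have pain scores at D0 and D10, and the named tests would ignore both in the D4 contrast.

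**Working it through.** **1. The plan's own figures.** Inputs from the Sample size paragraph: "Assuming a mean pain score on day 4 equals to 5 points with a standard deviation equals to 3 in the control group"; "to detect a difference of 2 points"; "with α (two-sided) = 2.5%, power= 90"%.

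- Two-sample t-test, standardised difference 2/3, two-sided alpha 0.025, power 0.90: n = 57.1, so 58 per group and 174 in total. This matches.
- Inflation: 58 × 1.1 = 63.8, so 64 per group and 192 in total. This matches.
- Allowance: (192 − 174)/192 = 9.4%, or 64 − 58 = 6 patients per arm.
- t-test power: 90.5% with 58 per arm, 93.2% with 64.

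The expected loss is therefore already covered for power. What remains is bias.

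**2. Size of a complete-case bias.** If a fraction m of an arm is missing and the missing patients' mean D4 pain differs from that of the observed patients by G, the observed arm mean is off by m × G. The documents give neither G nor the correlations between visits, so the following are assumptions: SD 3 at each visit (the plan's value for D4); correlations D0–D4 0.5, D4–D10 0.6, D0–D10 0.4; 10% missing; log-odds of missingness changing by 1 per SD of the driving score. Results are from simulation with 2 million patients per arm.

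| Missingness driven by | G (points) | Complete-case bias per arm | Bias left after regression on D0 and D10 |
|---|---|---|---|
| D10 pain | about 1.6 | 0.10 × 1.6 = 0.16 | about 0 |
| D4 pain itself | about 2.7 | 0.10 × 2.7 = 0.27 | about 0.16 |

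**3. Effect on the D4 difference, first row.**

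- Same pattern in both arms: 0.16 − 0.16 = 0.
- One arm only: 0.16 points, which is 0.16/2 = 8% of the 2-point target.
- Opposite directions: about 0.33 points (0.162 + 0.164), or 16% of the target.

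**4. Effect on type I error.** With 58 per arm the standard error of the difference is 3 × √(2/58) = 0.557. Under the null, a shift of 0.16 raises the two-sided error of one comparison from 0.025 to about 0.031. A shift of 0.33 raises it to about 0.05.

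**5. A different assumption.** With 5% missing in one arm and 15% in the other, and missing patients having 2 to 3 points more pain, the bias is (0.15 − 0.05) × 2 = 0.2 to (0.15 − 0.05) × 3 = 0.3 points. The error is then about 0.034 to 0.047.

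**The case against.** **The text excludes nobody.** The tests are listed generically, and the synopsis does not limit the D4 contact to one attempt. This stands: exclusion is a consequence of the named tests with no missing-data rule, not a written rule.

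**The SAP is still to come.** Missing-data handling is normal SAP content, and the SAP could settle the matter. This also stands, and the point is conditional on it. But nothing supplied gives a rule, and the trial is open-label, so the choice is better fixed early.

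**The 10% allowance proves nothing.** A reader might infer that it contradicts ITT or that the sample size is wrong. The documents support neither. The allowance is ordinary inflation, the numbers reproduce, and the undefined term may also cover per-protocol exclusions.

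**Part of the remedy is already planned.** Completion rates and D10 pain are secondary endpoints, and D10 scoring applies to all patients. Patients without a phone number, or for whom regular follow-up is impossible, are not enrolled, which should limit missed calls. All true. D10 pain is unused only in the D4 contrast.

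**The bias figures can flatter the fix.** A reader might take 0.33 points as the expected bias and near-zero as what a model would leave. The 0.33 needs opposite-direction missingness in two arms. The near-zero residual needs missingness driven by D10 pain, which is the setting where a model using D10 must succeed. If D4 pain drives it, about 0.16/0.27, or roughly 60%, of the bias remains. Moreover, pain found at the D4 call is managed, so D10 pain in those who answer may not be a clean guide to D4 pain in those who do not.

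**Conclusion.** The concern holds in a limited form. As the synopsis stands, the primary ITT comparison will by default be complete-case, with up to about 6 of 64 patients per arm left out if all of the non-evaluable allowance falls on D4 scores. Sample size and power are not in question.

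The plausible bias is modest against a 2-point target: from nothing to about 0.33 points when missingness follows D10 pain, and about 0.27 per affected arm when it follows D4 pain. These sizes rest on assumed correlations and missingness patterns. The documents do not show that missingness will in fact differ by arm. The change is worth making because it is cheap and the data it needs are already scheduled.

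**What to change.** In the SAP, before the database is closed:

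1. Define ITT as all randomised patients, analysed in the arm to which they were allocated.
2. Replace the unadjusted test as the primary analysis with a baseline-adjusted method that uses D0 and D10 pain. One example is a repeated-measures model of D4 and D10 pain with D0 pain as covariate and arm-by-visit terms; equivalent multiple imputation would also serve. Report the D4 contrast of each e-health arm with control.
3. State that patients with neither a D4 nor a D10 score enter only through imputation or the sensitivity analysis.
4. Use the completion rates already planned to show D4 missingness by arm.
5. Add a sensitivity analysis that shifts missing D4 scores by a range of points, separately in each arm.

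The cost is SAP wording and a little more analysis, with no new visits, data or patients. The downside is reliance on a missing-at-random assumption, which management of pain at the D4 call may make imperfect. Step 5 shows how far the conclusion depends on it.

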---------------------------	---

	
 - To reduce social and territorial inequalities. - To assess satisfaction with specific study management. - To assess compliance.
Study endpoints	
Primary endpoint: Pain score assessed (by phone) via a numeric pain scale completed 4 days after biopsy (D4).
 
Secondary endpoints :
 
 - Pain score assessed using a numeric pain scale administered after to biopsy and during the consultation of results announcement (approximately D10). - Anxiety score assessed using a numeric anxiety scale administered after to biopsy, at 4 days (D4) and during the consultation of results announcement (approximately D10). - Esthetic impact score assessed using a numeric esthetic scale administered after to biopsy, at 4 days (D4) and during the consultation of results announcement (approximately D10). - Insomnia score assessed using the Index of Severity of Insomnia administered during the baseline visit and the consultation of results announcement (approximately D10). - Number of alerts that generated a phone call or number of phone calls generated directly by the patient and patient care accordingly. - Quantity, nature and dose of analgesics, anxiolytics, anti-depressants, anti-inflammatory and hypnotics used for the biopsy and its aftermath. - Adverse event in particular bleeding and infection due to biopsy recorded at 4 days (D4) and during the consultation of results announcement (about D10) by NCI-CTCAE 5.0 - Geographical distance from the reference center. - Number of tablets/4G keys made available to patients who do not benefit from them at home. - Number of positive responses to satisfaction questions related to the number of solicitations for the study and how interventions are communicated - Rate of completion questionnaire and numeric scale.

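### The plan names only unadjusted tests for D4 pain and the other scores; adjusting for the D0 score already collected is a low-cost gain in precision, not the correction of an error

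*Combined protocol and SAP*

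**What the plan says.** Under Statistical considerations, the primary analysis is described in one sentence: "The primary endpoint, pain score assessed by phone 4 days after biopsy, will be compared between control and experimental arms". It covers each experimental arm against control but states no test, model or covariate. The general methods paragraph lists "the Student test or Wilcoxon / Kruskal-Wallis test for continuous parameters", with no rule for choosing among them. On populations it says "All statistical analyses will be performed on ITT population and on PP (per-protocole) population for primary endpoint". Further detail is deferred: "A statistical analysis plan (SAP) will be written before the closed database".

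The sample size paragraph states that "it is necessary to include 58 patients per group (174 patients in total), to detect a difference of 2 points", and then "Finally, 192 patients will be included considering 10% non-evaluable patients".

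Baseline information is collected. The scheme under Treatment modalities enters pain, anxiety and esthetic impact scores at D0, the point common to the three arms and on the same line as randomization. Study endpoints lists "Pain score assessed using a numeric pain scale administered after to biopsy and during the consultation of results announcement", with similar entries for anxiety and esthetic impact, and an insomnia index at the baseline visit. It also lists "Rate of completion questionnaire and numeric scale" as an endpoint, so some incompleteness is expected. No section uses a D0 or baseline score as a covariate or says how a missing one is handled.

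**The concern.** If pain just after the biopsy predicts pain four days later, part of the D4 variation can be explained before the arms are compared. An unadjusted test leaves that part in the error term. The trial then reports wider intervals than the same patients could support, in both primary comparisons and in the secondary scores that have a baseline value.

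Two things decide whether adjustment helps. First, a model that drops patients without a D0 score can lose more than it gains, and it departs from the ITT intention. Second, this trial is open-label and the plan does not say whether D0 is scored before allocation is disclosed. A covariate influenced by knowledge of the arm could bias the adjusted estimate.

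The model also has to be fixed before data are seen. Choosing afterwards among ANCOVA, Student and Wilcoxon results would be selective.

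**Working it through.** **Inputs from the plan (Statistical considerations, Sample size):** difference 2 points, SD 3, two-sided alpha 2.5% per comparison, target power 90%, 58 per group.

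**Assumed, because the documents give neither:** the correlation r between D0 and D4 pain (0 to 0.5), and the share m of patients with a D4 score but no D0 score (5% or 10%), missing completely at random.

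**1. Reproduce the plan's figure.** For a two-sample t-test, the noncentrality is 2 / (3 × √(2/58)) = 3.59, with 114 degrees of freedom and critical value 2.271.
- Power is 0.9047 at 58 per group and 0.8993 at 57, so 58 is exactly the t-test size. The normal approximation gives 56.
- The 97.5% CI half-width is 2.271 × 3 × √(2/58) = 1.27 points.
- Inflation: 174 × 1.10 = 191.4, hence 192, or 64 per arm.

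**2. Adjust for D0, all scores present.** Residual SD = 3 × √(1 − r²), with 113 degrees of freedom. This is 2.94, 2.86 and 2.60 at r = 0.2, 0.3 and 0.5.

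**3. Missing D0 scores imputed by the overall mean.** All 58 per arm stay in. The covariate explains only r²(1 − m) of the variance, so residual SD = 3 × √(1 − r²(1 − m)).

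**4. Missing D0 scores dropped (complete case).** Residual SD is as in step 2, with n = 58 × (1 − m), which is 52.2 at m = 10%.

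Power, with the CI half-width in points:

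| r | t-test | ANCOVA, complete D0 | ANCOVA, 10% imputed | ANCOVA, 10% dropped |
|---|---|---|---|---|
| 0 | 90.5%, 1.27 | 90.5%, 1.27 | 90.5%, 1.27 | 86.9%, 1.34 |
| 0.2 | 90.5%, 1.27 | 91.7%, 1.24 | 91.5%, 1.24 | 88.3%, 1.31 |
| 0.3 | 90.5%, 1.27 | 93.1%, 1.21 | 92.8%, 1.21 | 90.1%, 1.27 |
| 0.5 | 90.5%, 1.27 | 96.8%, 1.10 | 96.3%, 1.11 | 95.0%, 1.16 |

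With 5% missing at r = 0.2, power is 91.6% imputed and 90.1% dropped.

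**5. Break-even for dropping patients.** The variance of the estimated difference changes by the factor (1 − r²)/(1 − m). This equals 1 when r = √m, that is r = 0.22 at 5% missing and r = 0.32 at 10%. Below that correlation, complete-case ANCOVA is worse than the t-test.

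**6. Simulation (20,000 two-arm normal trials per setting, 58 per arm).** With 10% of D0 missing, power for imputed ANCOVA, complete-case ANCOVA and t-test was 0.912, 0.879 and 0.904 at r = 0.2, and 0.960, 0.945 and 0.902 at r = 0.5. Type I error with imputation was 0.0226 to 0.0247 against a nominal 0.025.

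**The case against.** The strongest reply is that this is a preference. The planned test is valid and meets its power target, no aim of the trial fails without ANCOVA, and nothing in the documents supports r near 0.5. At r = 0.2 to 0.3 the half-width falls by only 0.03 to 0.06 points. That stands, and it is why the point is framed as an efficiency gain. On the other side, the SD of 3 comes from a 25-patient pilot. If the true SD were 3.5 (an assumption), unadjusted power at 58 per arm would be 79%, against 83% with ANCOVA at r = 0.3 and 90% at r = 0.5.

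A second reply is that the missing-D0 risk arises only from the proposal, and that the 10% loss in the table may double-count. The 58 per group is already net of the non-evaluable allowance (64 × 0.9 = 57.6). If missing D0 scores fall within that allowance, complete-case power is 90.3% at r = 0 and 91.5% at r = 0.2. This is fair: the dropped-patient column describes an additional loss. With imputation the question does not arise.

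Third, D0 collection in every arm is read from the common D0 entry in the scheme; only D4 and D10 are explicitly said to cover all patients. The reading is very likely right but should be confirmed.

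Fourth, the SAP is deferred and Study period puts the end of follow-up in December 2023, so a SAP may already exist. Any such SAP should be checked first. Missing D4 scores also need a rule; that is a separate question.

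**Conclusion.** The point holds as a recommended improvement, not as an error. The unadjusted comparison is sound at 90.5% power. Adjusting for D0 pain costs almost nothing at r = 0, gives a small gain at r of 0.2 or less, and becomes material from about r = 0.5 (96.8% power, half-width 1.10 instead of 1.27 points). The sizes rest on the plan's SD of 3 and 2-point difference, on normal data, and on assumed values of r and of the missing-D0 share. The conclusion also requires that patients without a D0 score are kept and that D0 scores are recorded before allocation is known. Whatever r is, naming one primary model and one unadjusted test closes the open choice between Student and Wilcoxon.

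**What to change.** In the SAP, before data are seen:

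1. Pre-specify as primary a linear model of D4 pain on arm and D0 pain. Report each difference from control in points with a 97.5% confidence interval.
2. Keep every randomised patient who has a D4 score. Impute a missing D0 score, for example by the overall D0 mean computed without regard to arm, and report the number missing by arm.
3. Name the Student t-test, on which the 58 per group rests, as the single unadjusted sensitivity analysis.
4. Use the same model for D10 pain, D4 and D10 anxiety and esthetic scores, and D10 insomnia, each with its own baseline score.
5. State that D0 scores are baseline values, described but not tested between arms.
6. State whether D0 scores are recorded before allocation is disclosed. If this cannot be confirmed, make the t-test primary and ANCOVA the sensitivity analysis.

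The cost is SAP text, one line in the list of tests under Statistical considerations, and a check of how D0 scores were recorded. Item 5 also calls for a clarifying phrase in Study endpoints, where the post-biopsy scores now sit among the secondary endpoints to be compared. No extra patients, visits or scales are needed, and the planned 192 stays.
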